8.3 Unanticipated Problem Involving Risk to Subject or Other (UPIRSO)

Unanticipated problems will be submitted to IRB of record and the DSMC, according to local policies and procedures. An unanticipated problem is one that is unexpected, possibly, probably, or definitely related to the research described in the paragraph above, and suggests the research places research participants or others at a greater risk of physical or psychological harm than was previously known or recognized.

Since this is an investigator-initiated study, the principal investigator is responsible for reporting unanticipated problems to any regulatory agency and to the IRB. The study investigators and coordinators follow participants per the schedule of events outlined in the [Study Calendar](#) to ensure protocol compliance, participant safety, and quality care. Any unanticipated problems detected will be promptly documented by the study coordinator and submitted to the IRB and DSMC within 5 calendar days of study staff's knowledge. These reviews would pick up any unanticipated negative trends among participants.

8.4 Subject Complaints

If a complaint is received by anyone on the study staff, it will be discussed with the study staff and will be addressed on a case-by-case basis. The PI will be notified of any complaints. Complaints will be reported to the IRB if indicated.

If the subject has questions about his or her rights as a study subject, wants to report any problems or complaints, obtain information about the study or offer input, the subject can call the Medical College of Wisconsin/Froedtert Hospital research subject advocate at [contact]. This information is provided to the subject in their consent.

9.0 STATISTICAL CONSIDERATIONS

9.1 Sample Size Determination and Accrual Estimates

This is a pilot patient outcome study with a sample size of N=35, which would result in a 10% margin of error and a 90% exact confidence interval for a true population proportion of TG men with increased risk of breast cancer (assuming that 4 out of 35 participants will be found to have an elevated BC risk). In the future, enrolling 125 TG individuals would allow investigators to obtain a 90% confidence interval with a margin of error of 5%.

The sample size is also in line with reaching our accrual goal within a one-year period, as it represents one third of the patient population currently seen by our plastic surgeons.

9.2 Analysis Plan

9.2.1 Analysis Population

Data from all participants will be used for endpoint analyses. Data from subjects who withdraw or discontinue will be not used.

9.2.2 Endpoint Analysis

Descriptive statistics will be used to summarize participant characteristics and study outcomes for the above study aims. Median and range will be used for summarizing continuous variables; counts and percentages will be used for categorical variables.

To assess and compare the self-perceived breast cancer risk with calculated risk for third primary endpoint, self-perceived risk will be compared to mean BC calculated risk using the Wilcoxon related sample test. Chi-squared tests will be used to assess patient factors associated with under and overestimating self-perceived risk.

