1.2 Rationale

The goals of this pilot study are to 1) determine the percent of TGNB persons undergoing chest masculinization surgery who have an elevated lifetime risk of BC development (>17%) or a pathogenic genetic mutation that increased the risk of BC development (BRCA1/2, ATM, etc.), 2) measure the percent who are at risk and say they would choose to undergo risk-reducing mastectomies as part of chest masculinization surgery, and 3) assess and compare self-perceived BC risk with calculated risk. The results of this study will substantially inform TGNB patients and surgeons on the utility of personalized BC risk assessment prior to chest masculinization surgery and the accuracy of self-perceived BC risk in TGNB persons. This project has the potential to set a new standard of care that all TGNB persons should undergo a personalized BC risk assessment prior to gender-affirming surgery.

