2.0 OBJECTIVES AND ENDPOINTS

This prospective, single-arm interventional pilot study is designed to test whether a breast cancer risk assessment, genetic testing (when applicable), and surgical oncologist consultation can inform those TGNB patients at elevated risk for breast cancer (BC) development to undergo risk-reducing mastectomies in tandem with their gender-affirming chest masculinization surgery. This study is expected to collect and analyze novel data that describes the prevalence of elevated BC risk in the TGNB population and the concordance between self-perceived BC risk and calculated risk, a pressing need for which little is known.

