2.2 Primary Endpoints

1. The percentage of all participants undergoing chest masculinization surgery who are at elevated lifetime risk of BC development (*i.e.*, >17%) and those who undergo genetic counseling. Lifetime BC risk will be estimated utilizing the Gail and IBIS models.
2. The percentage of those participants with moderate to high lifetime BC risk or pathogenic germline variant that say they would choose to undergo a risk-reducing mastectomy.
3. The accuracy of self-perceived BC risk, as measured by the Visual Analog Scale (VAS), and the personalized BC risk assessment taken after the VAS.

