APPENDIX 1. LIFETIME BREAST CANCER RISK ASSESSMENT FORM

Lifetime Breast Cancer Risk Estimation

Name: _____

Date: _____ /2022

Participant reported lifetime risk estimation: _____ %

Green arrow depicts is the average lifetime risk for cisgender women up to age 85.

Gail model reported lifetime risk estimation (for those 35 and older): _____ %

IBIS model lifetime risk estimation: _____ %

Gail Model: <https://www.mdcalc.com/calc/3647/gail-model-breast-cancer-risk>

IBIS Model: <https://ibis.ikonopedia.com>

APPENDIX 2. NCCN TESTING CRITERIA FOR HIGH-PENETRANCE BREAST AND/OR OVARIAN CANCER SUSCEPTIBILITY GENES

TESTING CRITERIA FOR HIGH-PENETRANCE BREAST AND/OR OVARIAN CANCER SUSCEPTIBILITY GENES
(This can include *BRCA1*, *BRCA2*, *CDH1*, *PALB2*, *PTEN*, and *TP53* among others. See GENE-A for a more complete list.)^{a,b,c,d}

Testing is clinically indicated in the following scenarios:

1. Individuals with any blood relative with a known pathogenic/likely pathogenic variant in a cancer susceptibility gene
2. Individuals meeting the criteria below but tested negative with previous limited testing (eg, single gene and/or absent deletion/duplication analysis) interested in pursuing multi-gene testing
3. **Personal history of cancer**
 - Breast cancer with at least one of the following:
 - Diagnosed at age ≤ 45 y; or
 - Diagnosed at age 46–50 y with:
 - ◊ Unknown or limited family history; or
 - ◊ A second breast cancer diagnosed at any age; or
 - ◊ ≥ 1 close blood relative^f with breast, ovarian, pancreatic, or prostate cancer at any age
 - Diagnosed at age ≤ 60 y with triple-negative breast cancer;
 - Diagnosed at any age with:
 - ◊ Ashkenazi Jewish ancestry; or
 - ◊ ≥ 1 close blood relative^f with breast cancer at age ≤ 50 y or ovarian, pancreatic, metastatic,^g intraductal/cribriform histology, or high- or very-high risk group (see NCCN Guidelines for Prostate Cancer) prostate cancer at any age; or
 - ◊ ≥ 3 total diagnoses of breast cancer in patient and/or close blood relatives^f
 - Diagnosed at any age with male breast cancer
 - Epithelial ovarian cancer^h (including fallopian tube cancer or peritoneal cancer) at any age
 - Exocrine pancreatic cancer at any age (See CRIT-3*)
 - Prostate cancer at any age with:
 - Metastatic,^g intraductal/cribriform histology, or high- or very-high-risk group (see NCCN Guidelines for Prostate Cancerⁱ);
 - Any NCCN risk group (see NCCN Guidelines for Prostate Cancer) with the following family history:

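### Primary endpoint 3 is accuracy of self-perceived risk, but the one named comparison is a Wilcoxon paired test, which does not estimate error size; no paired or absolute error is defined

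*Combined protocol and SAP*

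**What the plan says.** Section 2.2 gives the third primary endpoint as "The accuracy of self-perceived BC risk, as measured by the Visual Analog Scale (VAS"), set against the personalized risk assessment done afterwards. Section 2.0 expects the study to describe "the concordance between self-perceived BC risk and calculated risk", and Section 1.2 expects the results to inform patients and surgeons about "the accuracy of self-perceived BC risk in TGNB persons". Objective 3 in Section 2.1 is milder: it asks only that the two risks be assessed and compared.

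Section 9.2.2 offers three things that bear on this endpoint:

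- A paired test: "self-perceived risk will be compared to mean BC calculated risk using the Wilcoxon related sample test". No significance level or sidedness is stated.
- A general rule for descriptives: "Median and range will be used for summarizing continuous variables", with counts and percentages for categorical variables.
- Chi-squared tests for "patient factors associated with under and overestimating self-perceived risk". Neither class is defined.

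The Appendix 1 form records "Participant reported lifetime risk estimation" in percent, the same unit as the Gail and IBIS results, so a difference in percentage points can be computed for every participant. Neither Section 9.2.2, nor the data list in Section 6.5, nor the form names a paired difference, an absolute error, an agreement statistic or a tolerance.

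**The concern.** Accuracy is about how close each person's estimate lies to the calculated value. A signed-rank test asks something else: whether the differences are centred away from zero. The two can part company both ways. A group with large errors in both directions can give a non-significant result, and a group with tiny errors all in one direction can give a highly significant one.

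One of three primary endpoints would then have no stated estimate and no stated precision. The reported error summary would depend on choices made after the data are seen. The most likely misuse is reading a non-significant test as evidence that participants perceive their risk accurately. Section 1.2 intends the accuracy finding to inform patients and surgeons, so that misreading would matter.

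**Working it through.** **The plan's own figure.** Section 9.1 gives a 10% margin of error at a 90% exact interval, "assuming that 4 out of 35 participants will be found to have an elevated BC risk". The Clopper-Pearson 90% interval for 4/35 is 4.0% to 24.3%. Its half-width is (24.3 − 4.0)/2 = 10.1 points, so the figure reproduces. It concerns endpoint 1; the documents give no precision figure for endpoint 3.

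**What the test measures.** Let d = VAS % minus calculated risk %. The signed-rank statistic W+ is the sum of the ranks of |d| over participants with d > 0. With n = 35 and no ties, W+ runs from 0 to 35 × 36/2 = 630, and its null mean is 315. Multiplying every d by the same positive constant leaves all signs and ranks unchanged, so W+ and the p-value are unchanged. A sample whose errors are all ten times larger gives the same p-value. The test therefore cannot estimate error size.

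**Simulation.** Inputs are n = 35 (Section 9.1), two-sided 0.05 (assumed) and 10,000 replicates. All error distributions are assumed, because the documents give none. Units are percentage points.

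| Assumed differences | Typical absolute error | Rejected |
|---|---|---|
| Random sign × uniform 5 to 15 | mean 10.0 | 5.5% |
| Same, VAS floored at 0% | mean 9.7 | 6.1% |
| Normal, mean 0, SD 3 | mean 2.4 | 4.8% |
| Normal, mean 1, SD 1 | median 1.1 | more than 99.9% |

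The floored row adds the errors to 31 calculated risks evenly spaced from 8 to 17% and 4 from 18 to 32%. Only the 31/4 split comes from Section 9.1; the spacing is assumed. Repeat runs of the first two rows moved by less than one percentage point, so both are close to the nominal 5%. Balanced errors averaging 10 points and balanced errors averaging 2.4 points are rejected at nearly the same rate, while a consistent error of about 1 point is nearly always significant.

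**One constructed extreme.** On the same 31/4 values, suppose participants' estimates are the calculated risks in fully reversed order. The differences are then exactly symmetric, so p = 1.0 and the signed median is 0 by construction. The median absolute difference is 5.4 points, and the range of d is −24 to +24. The sign split is 17 under, 1 exact, 17 over. This shows what the p-value and the signed median can miss; it is not a forecast.

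**Under and over.** Compare that sample with one in which every estimate is within 0.5 points, with alternating sign. Classed by sign, they are 17/1/17 and 17/0/18 (under/exact/over), almost the same. With an illustrative tolerance of 3 points they become 12/11/12 and 0/35/0, and at 5 points 9/17/9 and 0/35/0. The rule chosen therefore changes what enters the chi-squared tests.

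**Precision available at n = 35.** A distribution-free interval for a median runs between two ordered values, with coverage given by the Binomial(35, 0.5) distribution. Ordered values 13 and 23 give P(13 ≤ X ≤ 22) = 91.0%, in line with the 90% level of Section 9.1. Ordered values 12 and 24 give P(12 ≤ X ≤ 23) = 95.9%.

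**The case against.** The strongest reply is that Section 9.2.2 commits to more than a p-value. Chi-squared tests on under- and overestimation require each participant to be classed, and categorical variables are to be reported as counts and percentages, so the numbers of under- and overestimators would naturally appear. Continuous outcomes get a median and a range. If applied to the paired difference, the range does not cancel: in the reversed example it would show −24 to +24, and the counts would show errors in both directions. The Wilcoxon test also fits objective 3 as worded.

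This stands. A reader might infer that the plan will reveal only average over- or underestimation, and the documents do not support that. What remains is narrower. The paired difference is not named, medians of the two risks taken separately do not give paired error, counts give direction without size, and a range reflects only the two extremes.

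Three further points also stand:

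- The balanced-error scenarios fix the signs at 50/50. With a floor at 0%, large errors have more room upward, and the test would then tend to detect a shift. The scenarios show what is possible, not what is likely.
- A split of under and over by sign is workable apart from exact ties, so a tolerance is a choice to be stated rather than a necessity.
- This is a 35-person single-arm pilot. The paired values are collected, and no decision rule rests on endpoint 3.

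**Conclusion.** The concern holds in a limited form. The endpoint is accuracy, the only named comparison of VAS with calculated risk tests for systematic bias, and no measure of individual error is specified. Its size is illustrative: at n = 35 and an assumed two-sided 0.05, sign-balanced errors of 5 to 15 points are rejected about 5 to 6% of the time, and errors with mean 1 and SD 1 almost always. The error distributions, the spacing of calculated risks and the significance level are assumptions. The scale-invariance argument depends on none of them.

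A reader might go further and infer that the Wilcoxon test is the wrong test, or that participants' errors will in fact cancel. The documents support neither: the test suits objective 3, and they give no distribution of differences. The point should be fixed because it concerns a primary endpoint and the repair is cheap. The collected data remain usable either way.

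**What to change.** In Section 9.2.2:

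1. Define the paired difference as VAS % minus the calculated risk of Section 6.2: IBIS alone under age 35, the mean of Gail and IBIS from 35. This also settles the reference to a mean calculated risk, which Section 6.2 says is not computed under 35.
2. Report the median absolute difference with a confidence interval as the accuracy estimate. With 35 complete pairs, use ordered values 13 and 23 for about 91%, in line with Section 9.1, or 12 and 24 for 95.9%; state which.
3. Report the signed median difference with its interval.
4. Keep the Wilcoxon test, described as a test of systematic bias only.

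As a secondary clarification, state before analysis whether under and over are split by sign or by a justified tolerance in percentage points, and use that rule in the chi-squared tests.

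The cost is a few lines of SAP text and code, plus a justification if a tolerance is chosen. No new data are needed: the VAS, Gail and IBIS values are already on the data list. Sample size is unaffected.

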9.3 Missing Data

No major missing data relevant to the primary endpoints are anticipated. Unforeseen missing data, if any, will be addressed in consultation with the study statistician.

10.0 DATA AND SAFETY MONITORING PLAN (DSMP)

10.1 Data and Safety Management Overview

The Medical College of Wisconsin (MCW) Data Safety Monitoring Committee (DSMC) and the MCW Institutional Review Board (IRB) will approve protocol-specific DSM plans. A local, investigator-initiated trial will be required to be continuously monitored by the principal investigator of the study with biannual safety and progress reports submitted to the DSMC.

The DSMP for this study will involve the following entities:

10.2 Study Team

The study team minimally consists of 1) the principal investigator, [name], 2) a nurse practitioner, [name], APNP, who is a co-investigator on the study, and 3) the study biostatistician. While subjects are on treatment, the principal investigator will meet periodically with the rest of the study team to review the study status. This review will include but not be limited to reportable SAEs and UPIRSOs and an update of the ongoing study summary that describes study progress in terms of the study schema. The appropriateness of further subject enrollment and the specific intervention for a next subject enrollment is addressed. All meetings including attendance should be documented.

10.3 Quality Assurance

The MCWCC Clinical Trials Office (CTO) provides ongoing quality assurance audits.

This study has been categorized as low risk by the MCW Cancer Center (MCWCC) Scientific Review Committee (SRC) and will be reviewed internally by the MCWCC CTO Quality Assurance Staff according to the MCWCC [Data and Safety Monitoring Plan](#) and the current version of the MCWCC CTO SOP, [6.5.2 Internal Quality Assurance Reviews](#).

10.4 DSMC

The Medical College of Wisconsin Cancer Center places the highest priority on ensuring the safety of subjects participating in clinical trials. Every cancer interventional trial conducted at MCW includes a plan for safety and data monitoring.

More information can be found related to the MCWCC Data and Safety Monitoring Plan at the MCWCC website ([Data and Safety Monitoring Plan](#)).

This study will be reviewed by the Medical College of Wisconsin Cancer Center Data and Safety Monitoring Committee (MCWCC DSMC). A summary of the MCWCC DSMC activities are as follows:

- Review the clinical trial for data integrity and safety.
- Review all DSM reports.
- Submit a summary of any recommendations related to study conduct.
- Terminate the study if deemed unsafe for the subject.

A copy of the MCWCC Data and Safety Monitoring Plan and membership roster will be maintained in the study research file and updated as membership changes. The committee will review reports from the study principal investigator twice annually (or more frequently if needed) and provide recommendations on trial continuation, suspension or termination as necessary.

Any available DSMC letters will be submitted to the IRB of record as required.

11.0 REGULATORY COMPLIANCE, ETHICS, AND STUDY MANAGEMENT

11.1 Ethical Standard

This study will be conducted in accordance with the ethical principles that have their origin in the Declaration of Helsinki as stated in 21 CFR §312.120(c)(4), consistent with GCP and all applicable regulatory requirements.

11.2 Regulatory Compliance

This study will be conducted in compliance with:

- The protocol.
- Federal regulations, as applicable, including 21 CFR §50 (Protection of Human Subjects/Informed Consent); 21 CFR §56 (Institutional Review Boards) and §312 (Investigational New Drug Application; and 45 CFR §46 Subparts A (Common Rule), B (Pregnant Women, Human Fetuses and Neonates), C (Prisoners), and D (Children), GCP/ICH guidelines, and all applicable regulatory requirements. The IRB must comply with the regulations in 21 CFR §56 and applicable regulatory requirements.

11.3 Informed Consent Process

Informed consent is a process that is initiated prior to the individual agreeing to participate in the study and continues throughout the individual's study participation. Discussion of the risks and possible benefits of this study will be provided to subjects and their families. Consent forms describing in detail the study objectives, procedures, and risks are given to the subject and documentation of informed consent is required prior to enrollment. Consent forms will include the MCW IRB template language and must be approved by the MCW IRB.

The patient will be asked to read and review the document. Upon reviewing the document, the investigators will explain the research study to the patient and answer any questions that may arise. In accordance with 46 CFR §46.111, the patient will sign and date the informed consent document prior to any procedures being done specifically for the study. A witness should only sign when required, per FH/MCW IRB policy. The subjects will have the opportunity to discuss the study with their surrogates or think about it prior to agreeing to participate. The subjects may withdraw consent at any time throughout the course of the trial.

If the patient signs the consent form, the original signed document will become part of the patient's medical records and the patient will receive a copy of the signed document.

11.4 Subject Confidentiality and Access to Source Documents/Data

Subject confidentiality is strictly held in trust by the principal investigator, participating investigators, and any staff. This confidentiality includes the clinical information relating to participating subjects, as well as any genetic or biological testing.

The study protocol, documentation, data, and all other information generated will be held in strict confidence. No information concerning the study or data will be released to any unauthorized third party without prior written approval of the principal investigator. The conditions for maintaining

confidentiality of the subjects' records are required for the life of the data. These rules apply equally to any and all MCWCC projects.

The principal investigator will allow access to all source data and documents for the purposes of monitoring, audits, IRB review and regulatory inspections.

The study monitor or other authorized representatives of the principal investigator may inspect all documents and records required to be maintained by the investigator, including but not limited to, medical records (office, clinic, or hospital) and pharmacy records for the subjects in this study. The clinical study site will permit access to such records.

11.5 Risk-Benefit Assessment

11.5.1 Potential and Protections Against Risks

There is the potential for participant anxiety or distress regarding the results of their personalized BC risk assessment and/or their genetic test results. Our study team will do our best to answer questions and assuage concerns regarding anxiety or distress of testing results, we are also supported by the psychiatry and social work teams in the Clinical Cancer Center.

Another risk of taking part in a research study is that more people will handle the personal health information collected for this study. The study team will make every effort to protect the information and keep it confidential (see [Section 10.1](#)), but it is possible that an unauthorized person might see it. Depending on the kind of information being collected, it might be used in a way that could embarrass the subject or affect his/her ability to get insurance.

